- Final participant preferences- participants can be contacted to complete the surveys and final lens preference,
 - .1 Dry eye symptoms assessed (OSDI questionnaire), contact lens comfort assessed (CLDEQ). [for research purposes]
 - .2 Participant final selection of lens of choice #1 or #2 [for research purposes].
 - .3 Participant final selection of lens of choice #1 or #2 given average self-pay cost of annual replacement [for research purposes].
- Unscheduled visits
 - Will tally unscheduled visits and current lens type. [standard of care]

For Studies that Collect Prospective Data

- Data will be collected prospectively from the electronic medical record using paper care report forms and RedCAP by the primary and co-investigators at all study sites.
- A master list will be used to code participants and maintain study documents with study ID only. The list will be maintained by the investigator at each study site. De-identified data only will be shared with co-investigators listed on the study and with the locations listed on this study. The list will be stored in a locked cabinet of a locked office.
- At the completion of the study, the lists will be destroyed.
- De-identified data only will be maintained for future research use.

Survey studies

- Participants will complete the validated 12-item OSDI¹⁰ and the Contact lens dry eye questionnaire-8 (CLDEQ-8)¹¹ and comfort scale of contact lens performance to assess dry eye symptoms at each study visit.
- The OSDI Score is assessed on a scale of 0 to 100 with higher scores representing greater disability.

Studies involving use of product

- Two products will be used in this study.
 - Contact lens #1: SynergEyes VS (Synergeyes, Inc., Carlsbad CA) which features bi-tangential toric peripheries with linear landing zones. The standard lens is 16.0mm and is available from 14.5 to 17.5mm diameters.
 - Contact lens #2: RoseK2 corneal gas permeable lens (Blanchard Contact Lens, Inc. Manchester, NH). The lens is available in with a base

Initial correction keratoconus: corneal gas permeable vs scleral lens

curve range from 4.30 to 8.60 mm, diameter of 7.90 to 10.40mm.

- Product information including lens order number, lens parameters, lens materials and verification will be tracked and maintained in the case report form and on RedCAP.
- Adverse events will be recorded and immediately reported to the clinic PI.

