
APPENDICES

A. Eligibility Checklist

- Diagnosis of keratoconus confirmed by slit lamp and topography.
- No history of corneal surgery or INTACS (history of CXL okay)
- No prior history of prior hybrid, corneal or scleral gas permeable lens use.
- Age 18 or older
- Willing to return for 4 study visits.

Recruitment script:

“You may qualify to participate in a research study for patients with keratoconus with corrective contact lenses. As part of the study, participants are fit with two types of contact lenses and asked questions about their experience with each lens type. If you are interested in hearing more about the study I can provide more information and a copy of the written informed consent which outlines more details of the study. If you are not interested in participating in the study there will be no negative impact on your ongoing care.

B. Data Collection Forms

Study ID #

Date of signed informed consent

Randomization lens #1 →#2 or lens #2 →#1

*Odd # study id will begin with lens #1.

- Study visit number 1
 - .1 Patient demographics
 - .1.1 Age
 - .1.2 Race
 - .1.3 Age diagnosed with keratoconus
 - .2 Past ocular and medical history including ocular procedures such as corneal collagen crosslinking and corneal surgery.
 - .3 Best corrected visual acuity with manifest refraction
 - .4 Corneal curvature using topography
 - .5 Corneal pachymetry (thickness)
 - .6 Meibography

Initial correction keratoconus: corneal gas permeable vs scleral lens

- .7 *OSDI questionnaire*
- .8 *CLDEQ questionnaire*
- .9 *Lens fitting data*
 - .9.1 *Trial lens*
 - .9.2 *CL fitting evaluation*
 - .9.3 *Over refraction and best corrected visual acuity.*
 - .9.4 *Subjective comfort with lens use rated on comfort scale of 0 (not comfortable) to 10 (very comfortable)*
- *Study visit number 2*
 - .1 *Randomization: lens type corneal gas permeable or scleral lens*
 - .2 *Time started/finished lens application and removal handling*
 - .3 *Best corrected visual acuity with lens #1*
 - .4 *Subjective comfort with lens use rated on comfort scale of 0 (not comfortable) to 10 (very comfortable)*
- *Study visit number 3*

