 - .1 *Best corrected visual acuity with lens #1*
 - .2 *Hours of lens wear today, average hours of lens wear time, days per week of per week and daily time spent on lens application and removal*
 - .3 *Subjective comfort with lens use rated on comfort scale of 0 (not comfortable) to 10 (very comfortable)*
 - .4 *OSDI questionnaire*
 - .5 *CLDEQ questionnaire*
 - .6 *Time started/finished application and removal handling*
 - .7 *Best corrected visual acuity with lens #2*
 - .8 *Subjective comfort with lens use rated on comfort scale of 0 (not comfortable) to 10 (very comfortable)*
- *Study visit number 4*
 - .1 *Best corrected visual acuity with lens #2*
 - .2 *Hours of lens wear today, average hours of lens wear time, days per week of per week and daily time spent on lens application and removal*
 - .3 *Subjective comfort with lens use rated on comfort scale of 0 (not comfortable) to 10 (very comfortable)*
 - .4 *OSDI questionnaire*
 - .5 *CLDEQ questionnaire*
 - .6 *Participant final selection of lens of choice #1 or #2*
 - .7 *Participant final selection of lens of choice #1 or #2 given average self-pay cost of annual replacement.*

Non-study visits

Lens #1- number of lenses needed to finalize

Lens #2- number of lenses needed to finalize

Unscheduled visits

.1 Study ID

Date

Reason for unscheduled visit

Lens type unscheduled visit is related to (corneal gas permeable or scleral lens)

Lens loss

Lens breakage

Other problem (describe)

Len cessation advised? Yes/No

Adverse Event reporting

Study ID

Date

Type of adverse event:

Medical treatment required:

Len cessation advised? Yes/No

Questionnaires

OSDI 12

CLDEQ-8

Initial correction keratoconus: corneal gas permeable vs scleral lens

Ocular Surface Disease Index[®] (OSDI[®])²

Ask your patients the following 12 questions, and circle the number in the box that best represents each answer. Then, fill in boxes A, B, C, D, and E according to the instructions beside each.

Have you experienced any of the following during the last week ?	All of the time	Most of the time	Half of the time	Some of the time	None of the time
1. Eyes that are sensitive to light? . .	4	3	2	1	0
2. Eyes that feel gritty?	4	3	2	1	0
3. Painful or sore eyes?	4	3	2	1	0
4. Blurred vision?	4	3	2	1	0
5. Poor vision?	4	3	2	1	0

Subtotal score for answers 1 to 5

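### The adverse event form has no lens-type field, so events at visit 1, in the fitting phase or on the day of visit 3 cannot be reliably assigned to a lens

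*Protocol*

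**What the plan says.** Section 6.0 of the Protocol (studies involving use of product) states: "Adverse events will be recorded and immediately reported to the clinic PI". Sections 11.0 and 13.3 add review and reporting times. None of these sections asks for an event to be linked to a lens.

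The adverse event form in Appendix B has five entries: study ID, date, "Type of adverse event", "Medical treatment required", and a yes/no on whether stopping lens wear was advised.

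Unscheduled visits are handled differently. Section 6.0 says: "Will tally unscheduled visits and current lens type". The matching form in Appendix B carries the entry "Lens type unscheduled visit is related to (corneal gas permeable or scleral lens".

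The visit 2 form in Appendix B records the first lens by name: "Randomization: lens type corneal gas permeable or scleral lens".

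**The concern.** The trial has every participant use two devices, and its two event-type forms sit one above the other. The form that covers a lost or broken lens asks which lens it was. The form that covers a corneal abrasion does not. If lens attribution is not collected at the time, later analysis can only infer it, and for some events there is nothing to infer it from.

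What is at stake is a plain description of adverse events by lens type. Section 6.0 calls the study a pilot for a larger randomized trial, so its forms are part of what is being tried out. Events in the both-lens windows would have to be left unassigned or guessed.

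**Working it through.** No arithmetic applies beyond counting. The check is whether the lens can be worked out from the study ID, the event date and the randomized order, taking each stage of the visit schedule in Sections 3.0 and 6.0 in turn.

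1. **Visit 1 and the fitting phase.** Both lens types are fitted in both eyes at visit 1, and routine fitting visits follow until the lenses are fit to dispense. Randomization comes only at visit 2, so the order says nothing about an event in this stage. Result: not assignable from the form.
2. **Wear period 1 (from dispensing at visit 2, 2 to 4 weeks).** One lens type is in use, and the visit 2 form names it. Result: assignable.
3. **Day of visit 3.** The participant arrives having worn the first lens for at least 3 hours, is assessed in it, and is then trained in and wears the second. The form has a date but no time, so one date covers two lenses. Result: not reliably assignable.
4. **Wear period 2 (after visit 3, 2 to 4 weeks).** The first lens has been handed back. A participant who refuses to return it leaves the study. One lens type is in use, and it is the one not named at visit 2. Result: assignable.

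**Count.** Two of the four study visits (1 and 3) plus the fitting phase are ambiguous. The two wear periods, together 2 + 2 = 4 to 4 + 4 = 8 weeks, are not.

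**Can the crossover be dated?** The visit 2 to 4 lists in Appendix B show no date entry. However, the questionnaire pages carry a date line, and the questionnaires are completed at visits 3 and 4. The visit 3 date is the crossover date. Section 6.0 also draws data from the electronic medical record, which should supply the visit 2 date.

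**Does the lens numbering matter?** Section 6.0 lists "Contact lens #1: SynergEyes VS", and the allocation note in Appendix B, "Odd # study id will begin with lens #1", fits that product numbering. The visit schedule uses the same label for whichever lens is dispensed first. The derivation above does not depend on the number, because the visit 2 form uses the lens name. The conflict is a separate matter. Here it is only a reason to word any new field by name.

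**Does the unscheduled-visit form close the gap?** It does when an event leads to such a visit, since it carries the study ID, a date and the lens type. An event noticed at visit 1, at a routine fitting visit or at visit 3 need not generate one.

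**The case against.** The strongest reply is that nothing the protocol sets out to do is harmed. Section 3.0 lists no safety outcome by lens, Section 9.0 compares acuity, comfort and lenses ordered, and Section 12.0 promises descriptive statistics only. This stands, and it limits the weight of the point. It does not remove the point, because no later analysis plan can restore a field that was never collected.

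Second, most time in daily wear is attributable, as shown above. This also stands. A reader might infer that harms cannot be compared between the lenses at all. The documents do not support that: the gap is confined to the both-lens windows.

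Third, a reader might infer that every routine fitting visit involves both lenses, or that the ambiguous windows are when handling injuries are most likely. Neither is stated. Section 6.0 says only that fit and acuity are evaluated at those visits. Handling training starts at visit 2 with one lens, and unsupervised handling falls in the single-lens periods.

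Fourth, a reader might want eye and relatedness entries too. Nothing suggests that the two eyes wear different types within a wear period, so a missing eye entry should not misassign a wear-period event. Relatedness, on which Sections 11.0 and 13.3 make IRB reporting depend, can be judged when the principal investigator reviews the event. Neither entry is needed for attribution to a lens.

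Finally, Appendix B may be only an outline, and the built REDCap form is not shown. It may already hold the field. In that case Appendix B only needs to match it.

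**Conclusion.** The point holds in a limited form. The adverse event form as listed omits the lens type that the neighbouring form collects. Events at visit 1, in the fitting phase and on the day of visit 3 therefore cannot be reliably assigned to a lens unless an unscheduled-visit form also exists. Events within the wear periods mostly can be.

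How many events are affected cannot be stated, because the documents give no event rate and no length for the fitting phase. The conclusion assumes that the form is used as listed and that the dates of visits 2 and 3 can be found. The primary outcome, final lens choice, is unaffected, and no planned comparison depends on the missing field. This is a minor improvement to a descriptive pilot.

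**What to change.** Add one entry to the adverse event form in Appendix B, and to its REDCap counterpart if it is not already there: *lens type the event is related to: corneal gas permeable / scleral / both / neither*. Name the lens or product and do not use the lens number. The unscheduled-visit form already has suitable wording to adapt. Adverse events can then be described by lens without reconstruction.

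The cost is one tick-box field, with no change to visits, procedures or sample size. Entries for eye and relatedness are optional.
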